Patient Information Sheet and Informed Consent

Official Title of the Study:

Knee Arthroplasty Surgery: Short-Term Effects of Robotic Assistance (ROSA).
Randomized Study.

Version: 3.0.

Date: March 20th, 2022

Principal Investigator: [name].

Site: Hospital Universitario Santa Cristina. Madrid, Spain.

Introduction

Total knee arthroplasty (TKA) is a common orthopedic surgical procedure. The survival rate of total knee prostheses is approximately 95% at 10 years and 90% at 15 years. Overall patient satisfaction is estimated at around 80%.

TKA failure is multifactorial, involving patient-related factors, implant design factors, and surgical technique. While patient-related risk factors and infection prevention protocols help reduce complications, current implant materials and designs are not a major cause of failure. Recent clinical series show that instability and malalignment are among the leading causes of early failure, which are primarily surgeon-dependent. Inadequate implant positioning, improper bone resection, or excessive or insufficient soft tissue release can be mitigated by improvements in surgical technique.

The goal of robotic assistance is to eliminate surgical inaccuracies and help execute the preoperative plan with precision. The robot positions and holds the cutting guide in place, assists with distal femoral cuts, determines prosthetic component sizes, and facilitates alignment and soft tissue balancing. The surgeon remains in full control of the saw and performs all bone cuts.

Robotic systems also enable intraoperative assessment of soft tissues, allowing the surgeon to implant the prosthesis in an anatomically adapted position, optimizing alignment and function. This increased precision may enhance early postoperative functional recovery compared to conventional TKA.

The ROSA surgical robot has been approved and commercially available since 2019. At Hospital Universitario Santa Cristina, the ROSA system has been used for TKA procedures since January 2021.

Objectives

Primary Objective:

To compare early functional recovery in patients undergoing TKA with robotic assistance versus conventional manual technique over the first three months after surgery.

Secondary Objectives:

- To analyze length of hospital stay, laboratory parameters, joint range of motion (ROM), and pain in both groups.

- To evaluate mechanical recovery following robotic and manual TKA.
- To compare postoperative long-leg standing radiographs in both groups.

Materials and Methods

Study Design:

Prospective, randomized, controlled study involving two groups of patients undergoing TKA, all operated on by the same experienced surgeon skilled in both conventional and robotic-assisted techniques.

Patients will be selected from those on the hospital surgical waiting list who meet inclusion criteria. Selection is blind and conducted by the hospital's administrative service, independent of the principal investigator. Randomization will follow a parallel 1:1 model, using dice rolls.

Each group will include a minimum of 30 patients, enabling the use of parametric tests supported by the Central Limit Theorem.

Inclusion Criteria

- Patients with primary osteoarthritis indicated for TKA who provide informed consent.
- All patients will receive the same prosthesis model: Persona® (Zimmer Biomet), a posterior-stabilized primary knee prosthesis with patellar resurfacing, approved through public procurement.

Exclusion Criteria

- Previous surgery on the affected knee.
- Presence of other prostheses in the same limb.
- Hip pathology on the same side (e.g., dysplasia, avascular necrosis, arthrodesis, flexion contractures) that limits bone mass or mobility.
- Active infections near the affected knee joint.
- Obesity (BMI > 30).
- Dependent patients.
- Residents of long-term care facilities.
- Anatomical abnormalities, ligament instability, or severe femoral-tibial misalignment requiring alternative prosthesis models.

Surgical Protocol and Randomization

All patients will receive the same implant model: Persona[®] (Zimmer Biomet, Warsaw, Indiana, USA). Robotic-assisted surgeries will be performed with the ROSA[®] system (Zimmer Biomet, Warsaw, Indiana, USA).

After preoperative assessment, patients will be added to the surgical schedule. Scheduling occurs 15 days in advance and is managed by the department head. Once scheduled, randomization is performed using dice rolls:

- Even number: Robotic TKA (Group 1)
- Odd number: Manual TKA (Group 2)

Follow-up Schedule

All TKA patients at Hospital Universitario Santa Cristina are followed up weekly in outpatient clinics. First follow-up occurs at 2–3 weeks post-op; subsequent visits are at 2, 3, 6, 9, and 12 months. Annual visits continue for 5 years, then every two years until 10 years.

In this study, patients follow the same clinical follow-up schedule, although the study itself concludes at 3 months.

Variables

Demographic

Age, sex, and comorbidities (diabetes mellitus, hypertension, rheumatoid arthritis, ischemic heart disease, anticoagulation).

Laboratory Parameters

Hemoglobin, hematocrit, ESR, CRP, and D-dimer levels will be recorded preoperatively, on the day of surgery (before and after the procedure), and at hospital discharge. Drain output (mL) during the first 24 hours post-op will also be recorded.

Surgical Parameters

Surgery duration (minutes), intraoperative complications (fracture, ligament or vascular injury), surgeon-performed bone cut corrections, and the difference (mm) between planned and robot-measured resections.

Pain

Assessed daily using a visual analog scale (VAS) during clinical rounds and recorded in the hospital's electronic medical record (HP-HCIS).

Length of Hospital Stay

Number of days from hospital admission for surgery to discharge, obtained from HP-HCIS.

Functional Recovery

Assessed using KOOS and SF-36 questionnaires preoperatively and at 2 and 3 months after surgery.

Joint Range of Motion

Measured daily with a goniometer and recorded in degrees of flexion and extension in the HP-HCIS.

Mechanical Recovery

Evaluated via surface electromyography (EMG) performed before surgery and at 3 months post-op using the Myomed 932 EMG device. Electrodes are placed over target muscle bellies, and both isometric (5-second contractions and rest, 1 minute) and isotonic (5 quick contractions and 5-second rest, 1 minute) protocols are performed. Peak and mean muscle strength are recorded.

Radiology

Preoperative AP/lateral X-rays and long-leg standing radiographs will be performed. Radiologic evaluation includes mechanical and anatomical axis, tibial slope, and osteoarthritis grade (Kellgren-Lawrence). Postoperative AP/lateral X-rays will be taken immediately post-op, at discharge, and at 2 and 3 months.

Data Management and Statistical Analysis

Data will be recorded in a coded database without personal identifiers. A separate confidential file linking study codes to patient identities (name, clinical ID, and national ID) will be kept by the principal investigator.

Patient outcomes will be analyzed over the 3-month period, comparing the evolution of each variable between groups. Descriptive statistics will be used, and group comparisons will be performed using Chi-square tests for binary variables. The CONSORT 2010 guidelines were followed in the preparation of the Methods section.

Ethical Considerations

All potential participants will be informed about the study during the preoperative consultation. An information sheet will be provided, and informed consent will be obtained prior to enrollment.

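### Only patient selection is described as blind; nothing in the available text keeps the arm from patients or outcome collectors, so the self-reported measure of the primary objective is open to expectation bias

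*Combined protocol and SAP*

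**What the plan says.** On blinding, Study Design has one statement: "Selection is blind and conducted by" the hospital's administrative service, separately from the principal investigator. It concerns who is taken from the waiting list.

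On allocation, the same section says "Randomization will follow a parallel 1:1 model, using dice rolls". Surgical Protocol and Randomization gives the order of events: preoperative assessment comes first, then entry on the surgical schedule. On timing it says "Scheduling occurs 15 days in advance and is managed by the department head", and then "Once scheduled, randomization is performed using dice rolls", with even numbers going to robotic and odd numbers to manual surgery.

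On outcomes, the primary objective is "To compare early functional recovery in patients undergoing TKA with robotic assistance versus conventional manual technique over the first three months after surgery". The Functional Recovery entry under Variables reads "Assessed using KOOS and SF-36 questionnaires preoperatively and at 2 and 3 months after surgery". Among the secondary measures, pain is "Assessed daily using a visual analog scale (VAS) during clinical rounds", range of motion is taken daily with a goniometer, EMG is recorded before surgery and at 3 months, and radiographs are evaluated for axis and slope.

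Data Management and Statistical Analysis provides for a coded database without personal identifiers, with the linking file held by the principal investigator. The Introduction suggests that robotic precision may improve early functional recovery relative to conventional surgery.

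**The concern.** Selecting patients blind does nothing to mask treatment, because no arm exists yet when names are picked. Once the die is rolled, the arm is known to someone at the hospital for up to about two weeks before the operation, and the plan has no rule on who may learn it.

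This matters because of how the main question is answered. KOOS and SF-36 scores are the patient's own report. The Introduction stands in a file headed as a patient information sheet. If patients read that text and also learn their arm, those given the robot have a reason to expect a better recovery and those given the manual technique a reason to expect a worse one. Either can move self-reported function without any mechanical effect.

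Randomization balances patients at entry; it does not remove a difference in reporting that arises after allocation. The bias would also run in the direction of the trial's hypothesis, so a favourable result could not be separated from it. VAS on ward rounds, goniometer readings and voluntary EMG contractions are exposed in a similar way, but they serve secondary objectives.

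**Working it through.** **Step 1. Who is masked, by role.**

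| Role | What the text says |
|---|---|
| Administrative service picking names | Selection called blind; no arm exists yet |
| Patient | Nothing on learning or not learning the arm |
| Operating surgeon | Cannot be masked |
| Staff recording VAS and range of motion | No masking stated |
| Whoever gives out KOOS and SF-36 | Not identified; no masking stated |
| EMG and radiograph assessors | Not identified; no masking stated |
| Analyst | No masking stated |

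The database code does not fill the gap. It is presented as protection of identity, the principal investigator holds the key, and nothing says that images or EMG traces are coded or that the arm is hidden.

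**Step 2. Timing.** The stated order is preoperative assessment, scheduling (15 days ahead), dice roll, surgery. The day of the roll is not fixed, so the interval from roll to surgery is at most about 15 days.

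**Step 3. Which measure serves the primary objective.** No variable is labelled as the primary outcome. The objective names functional recovery, and the variable of that name consists only of KOOS and SF-36. On that match, the primary comparison rests on self-report.

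**Step 4. Illustration of size.** The plan has no figure of its own to reproduce here. The 30 per group is a stated minimum; no alpha, sidedness, power, effect size or SD is given.

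Inputs:
- n = 30 per arm (Study Design).
- Two-sample t-test, two-sided 5% (assumed).
- True effect zero (assumed).
- Reporting shift b towards the robot, in SD units (assumed; not in the documents).

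Formulas: degrees of freedom = 2 × 30 − 2 = 58, critical value c = 2.002, noncentrality δ = b × √(30/2) = 3.873b. The chance of a significant result is P(T > c) + P(T < −c), where T is noncentral t with 58 degrees of freedom and noncentrality δ.

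| Shift b (SD) | δ | Chance of a significant result |
|---|---|---|
| 0 | 0 | 5.0% |
| 0.1 | 0.387 | 6.7% |
| 0.2 | 0.775 | 11.9% |
| 0.3 | 1.162 | 20.8% |
| 0.5 | 1.936 | 47.8% |

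As a cross-check, the normal approximation with standard error √(2/30) SD gives 6.7%, 12.1%, 21.3% and 49.1%. The small differences come from the approximation alone.

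**The case against.** The strongest reply is that this is silence, not a flaw in conduct. No sentence says that patients are told their arm, and a team could follow every line and still withhold it. A reader might infer that the plan followed as written must produce a biased comparison; the documents do not support that. They leave the comparison open to bias, which is the claim made here.

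A reader might also infer that baseline scores are collected after the patient knows the arm. The text points the other way, since preoperative assessment precedes scheduling and the roll. What remains is an ambiguity: the contents of that assessment are not listed, and KOOS, SF-36 and EMG are timed only as before surgery.

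Consent pages are not in the available file, so a statement there about disclosure of the arm cannot be excluded. That limits the point about patients. It does not explain why the Methods, which cite CONSORT 2010, neither say who is masked nor declare the trial open-label.

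The error rates are not evidence about this trial. At 0.1 SD the chance of a significant result is barely above 5%, and no source in the documents supports any particular shift. This stands, and the figures should be read only as a scale.

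Finally, it is fair to doubt that every masking step is free. The documents do not say who reads radiographs or records EMG, or how radiographs are measured, so masked reading may need someone other than the present assessor. That is why the fix makes that item conditional on existing staff.

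**Conclusion.** The concern holds in this form: the Methods describe blinding of patient selection only, the arm is set before surgery, and no rule in the available text keeps it from patients or outcome collectors, while the primary objective is measured by self-report. The comparison is therefore open to expectation bias favouring the robot. Under the assumptions above, a shift of 0.1 to 0.5 SD would raise the chance of a falsely significant result from 5% to between 6.7% and 47.8%; whether any such shift would occur is unknown.

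The conclusion rests on three readings: that KOOS and SF-36 are the measures of the primary objective, that the missing consent pages contain no masking rule, and that silence leaves disclosure to local habit. Because the surgeon cannot be masked, full blinding is not available, but masking of the patient for the three months of the study can be attempted. This should be changed before the trial's result is relied on. It does not show that the trial is invalid.

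**What to change.** Add to Study Design:

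1. The patient is not told the arm until the 3-month KOOS and SF-36 have been returned. The consent sheet should agree with this.
2. KOOS and SF-36 are completed by the patient alone, without the operating surgeon present.
3. At 3 months each patient is asked which arm they think they had, and the answers are reported by arm.
4. Baseline KOOS, SF-36 and EMG are stated to be part of the preoperative assessment that already precedes scheduling and the roll.
5. Where existing staff allow, radiographs and EMG are read with the arm label withheld. Otherwise the report states, as a limit on the conclusion, that those assessors are unmasked. The surgeon is named as unmasked in either case.

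Items 1 to 4 are protocol and consent wording plus one question at a visit already planned; they need no added staff or procedure. Item 5 depends on who does the reading, which the plan should state. The main downside is that masking may be imperfect and needs staff discipline for three months. Item 3 will help show how well it held.

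### The only blood sample after the day of surgery is taken at discharge, so a difference in stay between arms can appear as a laboratory difference

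*Combined protocol and SAP*

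**What the plan says.** All references are to the combined protocol and SAP.

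- **Laboratory Parameters** names five analytes: "Hemoglobin, hematocrit, ESR, CRP, and D-dimer levels will be recorded". The draws are "recorded preoperatively, on the day of surgery (before and after the procedure), and at hospital discharge". No postoperative day is attached to the last of them ("and at hospital discharge"). The same section adds a blood-loss measure: "Drain output (mL) during the first 24 hours post-op will also be recorded".
- **Length of Hospital Stay** is defined as "Number of days from hospital admission for surgery to discharge, obtained from HP-HCIS".
- **Objectives** puts both outcomes in one secondary objective: "To analyze length of hospital stay, laboratory parameters, joint range of motion (ROM), and pain in both groups".
- **Data Management and Statistical Analysis** says that the course of each variable will be compared between groups. It names descriptive statistics, and chi-square tests for binary variables. It does not mention time since surgery, and nowhere does the plan say that the postoperative day of the discharge draw will be recorded.
- **Follow-up Schedule** puts the first outpatient visit at 2–3 weeks, and no blood draw is listed for it.

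**The concern.** Any laboratory comparison of recovery beyond the operation day rests on one value per patient, and that value is drawn at an outcome-dependent time. Randomisation makes the arms comparable on any given postoperative day. It does not make them comparable on the day of discharge, because discharge comes after allocation and may be affected by it.

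The trial is run because robotic assistance may speed early recovery. If it does, stay may shorten in that arm, and its discharge samples would then come from an earlier recovery day. For a marker still falling at that point, such as CRP under the assumption used below, the arm that leaves earlier would show the higher value with no biological difference on any fixed day. For other analytes the direction depends on whether they are rising or falling at discharge, which the documents do not say.

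What is at stake is the interpretation of secondary laboratory outcomes. The primary objective, functional recovery over three months, is not touched.

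**Working it through.** **Plan's own figure.** The only design number is the minimum of 30 per group (Study Design). It is justified by the Central Limit Theorem, with no alpha, power, effect size or SD, so it cannot be reproduced from a power calculation. It enters here only as n.

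**Inputs.** From the plan: n = 30 per arm, 1:1 allocation, draw at discharge. Assumed, because the documents give no figure:

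- CRP falls 20–40% per day near discharge.
- Between-patient SD of log CRP on a fixed day is s = 0.5–0.75.
- Postoperative stay has SD 1.5 days in each arm, independent of CRP level.
- Mean stay differs by d = 0.5 or 1 day.
- Arms are compared by a two-sided 5% t-test on log CRP. The plan names no test for this outcome.
- There is no true difference on any fixed day.

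**Formulas.**

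1. Daily change on the log scale: b = −ln(1 − decline). This gives 0.223 at 20% and 0.511 at 40%.
2. Spurious log difference: b × d. As a ratio, (1 − decline)^(−d) = 1.12–1.29 for half a day and 1.25–1.67 for one day.
3. SD of log CRP at discharge: √(s² + (1.5b)²). Stay spread contributes 1.5 × 0.511 = 0.77 on its own at a 40% decline.
4. Noncentrality: (b × d / SD) × √(30/2). The rejection probability comes from the noncentral t with 58 degrees of freedom.

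| Decline/day | s | SD at discharge | Rejection, d = 0.5 | Rejection, d = 1 |
|---|---|---|---|---|
| 20% | 0.50 | 0.602 | 10.9% | 29.2% |
| 20% | 0.75 | 0.821 | 8.1% | 17.9% |
| 40% | 0.50 | 0.915 | 18.6% | 56.6% |
| 40% | 0.75 | 1.072 | 14.8% | 44.2% |

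Worked case (40%, s = 0.50, d = 1): 0.511 / 0.915 = 0.558; 0.558 × √15 = 2.16; rejection 56.6%.

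The ranges are therefore about 8–19% and 18–57%. With b = 0 or d = 0 the noncentrality is zero and the rate is 5%.

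**Second check, other assumptions.** Take a linear drift in SD units per day, stay SD 1 day, 30 per arm, 20,000 simulated trials. With a one-day stay difference, discharge sampling rejected in 15% of trials at 0.25 SD/day and 40% at 0.5 SD/day. Sampling on a fixed day gave 4.8–5.5% across all the settings run, whatever the stay difference.

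**Length of stay.** Stay from admission equals the preoperative interval plus the postoperative stay. If the interval is constant, it cancels from the comparison. If it varies independently of postoperative stay, the variance is multiplied by 1 + (preoperative SD / 1.5)². At an assumed preoperative SD of 0.3–1.0 day this is 1.04–1.44. The documents give no interval, so this only shows what might be lost.

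**The case against.** **Postoperative laboratory data are anchored to surgery in part.** All five analytes are also drawn after the procedure on the operation day, and drain output covers a fixed 24 hours. A reader might infer that no postoperative laboratory comparison runs on a common clock. The documents do not support that: these two measures do not depend on stay. They describe only the immediate perioperative period, however, so the point stands for later values.

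**The bias is conditional.** It needs both a stay difference and an analyte still changing at discharge, and the plan quantifies neither. This objection stands in full: discharge sampling can create a spurious difference, and it cannot be said that it will.

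**The size depends on the spread of stay.** A reader who treats 0.5–0.75 as the whole SD of discharge log CRP would get 9–49% for half a day and 20–97% for one day. If the range describes patients on a fixed day, those figures leave out the variation that differing discharge days add, and the top end is inflated. The lower ranges in the working are the ones to use.

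**No test of discharge CRP is named.** This is correct. The t-test is an assumption, and the error rates apply only if such a comparison is made. The shift in means is there whichever summary is used.

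**Stay from admission is a uniform definition.** A reader might infer bias because the arm is known before admission. The documents do not support this. Surgery is already on the schedule when the dice are rolled ("Scheduling occurs 15 days in advance"), and nothing suggests an arm-dependent admission date. What remains is possible noise, so this half is minor.

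**Analysts could adjust for days since surgery.** None is planned, and that variable is itself affected by allocation, so adjustment is a weaker remedy than a fixed draw.

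**Conclusion.** The concern holds in a limited, conditional form. As written, the plan's only laboratory comparison after the day of surgery is tied to discharge, an outcome-dependent time, with no planned account of when the sample was taken. The false-positive rates in the working, up to 57% for a one-day stay difference, rest wholly on assumed inputs and on stay being independent of CRP level. They show how large the problem could be and do not estimate it for this trial. The claim that the faster arm is always penalised goes too far, since it follows only for a marker that is falling at discharge.

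Both outcomes are secondary and the remedy is cheap, so this should be corrected, but it does not threaten the primary objective. The definition of length of stay is a small tidying point.

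**What to change.** 1. In Laboratory Parameters, take the last comparative sample on one fixed postoperative day. The sponsor should choose the day so that nearly all patients are still in hospital.
2. If the discharge sample is kept, record its postoperative day and report it descriptively, without a comparison between arms.
3. As a minor addition, count length of stay from the date of surgery to discharge. This removes preoperative days, which cannot reflect surgical technique. It changes nothing if the admission-to-surgery interval is constant. The documents say that the stay count comes from the hospital record but do not say that the surgery date is held there, so the sponsor should confirm its source.

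**Cost.** This is a change of protocol wording. One draw moves, and none is added unless the discharge sample is kept as well. The drawback is that patients discharged before the fixed day would lack the sample, and these are the early leavers. The number missing should be reported by arm.

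### The primary objective has no deciding score, visit, significance level or decision rule; two unranked questionnaires at two postoperative visits are compared only in generic terms

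*Combined protocol and SAP*

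**What the plan says.** All places are in the combined protocol and SAP.

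- **Objectives, Primary Objective:** the stated aim is "To compare early functional recovery in patients undergoing TKA with robotic assistance versus conventional manual technique over the first three months after surgery". No instrument, score or visit is named.
- **Introduction:** the rationale is "This increased precision may enhance early postoperative functional recovery compared to conventional TKA". This also names no measure.
- **Functional Recovery:** "Assessed using KOOS and SF-36 questionnaires preoperatively and at 2 and 3 months after surgery". The two questionnaires are listed side by side, and no total, subscale or summary score is chosen.
- **Data Management and Statistical Analysis:** "Patient outcomes will be analyzed over the 3-month period, comparing the evolution of each variable between groups", followed by "Descriptive statistics will be used, and group comparisons will be performed using Chi-square tests for binary variables". No test or model is given for a questionnaire score.
- **Study Design:** "Each group will include a minimum of 30 patients, enabling the use of parametric tests supported by the Central Limit Theorem". Parametric tests are mentioned as a class, and none is assigned to an outcome.

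The Follow-up Schedule section ends the study at 3 months, which fixes the window but does not put the 3-month visit ahead of the 2-month visit. Alpha, sidedness, a multiplicity rule and a criterion for answering the primary objective are stated nowhere.

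**The concern.** A randomised comparison protects against chance findings only if the comparison that answers the question is fixed in advance. Here the question is fixed and the deciding comparison is not. The analyst could use KOOS or SF-36, any score within either, 2 months, 3 months or both, and change or final value. Each choice is consistent with the text.

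Two things are at stake. If any one significant result is taken to show a difference, the chance of a false positive is above that of a single test. And if one questionnaire is significant and the other is not, the plan gives no reading of that result, so the reading would be chosen with the data in view.

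**Working it through.** **No design figure to reproduce.** The plan gives 30 per group as a minimum, with no alpha, power, effect size or SD behind it. What follows measures the consequence of the open choice.

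**Inputs from the documents:** two questionnaires; two postoperative visits; at least 30 patients per group; 1:1 allocation.

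**Assumptions:** two-sided 5% per test; one score per questionnaire; 30 analysed per group; unadjusted t-tests; a true effect of 0.5 SD on every measure where power is considered; correlations shown as ranges. The documents name no score, so one per questionnaire is a minimum.

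**Step 1. How many tests?** The analysis section speaks of how each variable evolves over three months. That favours one longitudinal comparison per questionnaire, so two tests. Testing each visit separately, so four tests, is not excluded.

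**Step 2. Two tests, no true difference.** For standard normal test statistics with correlation ρ:

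- P(at least one significant) = 1 − P(|Z₁| ≤ 1.96 and |Z₂| ≤ 1.96)
- P(both significant) = 0.05 + 0.05 − P(at least one)

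At ρ = 0 the first is 1 − 0.95² = 0.0975.

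| ρ | at least one | both |
|---|---|---|
| 0 | 9.75% | 0.25% |
| 0.3 | 9.5% | 0.5% |
| 0.5 | 9.1% | 0.9% |
| 0.8 | 7.8% | 2.2% |
| 0.9 | 7.0% | 3.0% |

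The error rate depends on the unstated rule: above 5% if either result suffices, below 5% if both are required. The both column counts significance in any direction; at ρ = 0, half of the 0.25% are pairs pointing in opposite directions.

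**Step 3. Two tests, true effect 0.5 SD on both** (100,000 simulated trials). Mixed = P(at least one) − P(both), up to rounding.

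| questionnaire correlation | at least one | both | mixed |
|---|---|---|---|
| 0.3 | 67.9% | 27.6% | 40.3% |
| 0.5 | 64.7% | 31.0% | 33.7% |
| 0.6 | 62.8% | 33.1% | 29.7% |
| 0.8 | 58.1% | 37.4% | 20.8% |

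A single named t-test has noncentrality 0.5 × √(30/2) = 1.94 on 58 df, so its power is 47.8%.

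**Step 4. Four tests.** One correlation structure is used for both quantities: the (visit, questionnaire) correlation runs from (0.5, 0.3) to (0.9, 0.8), and the correlation across both is their product. With no true difference, at least one test is significant in about 17% to 11% of trials. With 0.5 SD on all four, some but not all are significant in about 71% to 35%.

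**Step 5. What one baseline-adjusted test gives.** Adjusting for a preoperative score with correlation r to the outcome divides the noncentrality by √(1 − r²), on 57 df.

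| r | noncentrality | power at 0.5 SD |
|---|---|---|
| unadjusted | 1.94 | 48% |
| 0.3 | 1.94/0.954 = 2.03 | 51% |
| 0.5 | 1.94/0.866 = 2.24 | 59% |
| 0.7 | 1.94/0.714 = 2.71 | 76% |

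The false-positive rate of this single test is 5%.

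**The case against.** The best defence is that the objective is neutral. It sets out to compare, not to prove superiority, and the plan states no hypothesis, success claim or power. The contrast is not absent either: a between-group comparison over three months is stated for every variable. On this view the error rates in steps 2 and 4 belong to a rule that the plan never adopts.

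Much of that stands.

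- A reader might infer that the plan has no contrast at all. It has one, but it is generic: no summary measure, model or time point is attached to it.
- A reader might infer that the sponsor will declare success on any significant result. The documents do not say so, and the inflated rates are conditional on that reading.
- A reader might infer that one dataset could support opposite conclusions. The calculations show significant against non-significant results, not effects in opposite directions.
- A reader might take 1 − 0.95⁴ = 18.5% as the four-test risk. That treats two visits one month apart on the same questionnaire as independent, which is not plausible.
- The equal standing of the questionnaires is inferred from the lack of any ranking; the plan does not assert it.

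What does not stand is the idea that a neutral objective needs no deciding comparison. A comparison still has to be read, and no section says which result answers the question.

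**Conclusion.** The concern holds in this form: the primary objective has no deciding score or visit, no alpha and no decision rule, and its contrast is only generic. That gap rests on the text alone and not on any assumed number.

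Its size does rest on the assumptions listed above. On the two-test reading, the false-positive risk is 9.8% to 7.0% instead of 5% if any one significant result is read as a difference, and the questionnaires disagree in about 40% to 21% of trials with a true 0.5 SD effect. On the four-test reading the figures are about 17% to 11% and about 71% to 35%. Selection among several scores within a questionnaire is not counted.

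A reader might extend the point to the group size, which the plan justifies by the Central Limit Theorem. The plan claims no power, so that is a separate disclosure matter of low severity and no part of this conclusion.

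**What to change.** Before any comparison of outcomes by group, amend the analysis section to name one primary comparison, tested once at two-sided 5%. Proposed content:

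- **Primary comparison:** the between-group difference in one KOOS score, averaged over the 2- and 3-month visits. The sponsor names the score before seeing unblinded data.
- **Model:** a linear repeated-measures model adjusted for the preoperative value of that score, so that patients with only one postoperative visit still contribute.
- **Decision rule:** only this test answers the primary objective.
- **Secondary:** all other KOOS scores, the single-visit comparisons and SF-36, each reported with a 95% CI.

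KOOS and the two-visit average are proposals, not readings of the plan. The average fits an objective that covers the whole three-month window, but another single pre-specified score and time point would also close the gap.

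**Cost:** amended wording only; the preoperative scores and both visits are already planned. SF-36 and the single visits lose equal standing, and averaging can hide a difference present only at 2 months. The documents do not show whether outcomes have already been compared by group. If they have, the choice must be labelled post hoc.
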